### **1.2.1. Analysis Timepoint(s)**

Following premature study termination, there will be only 1 Analysis Timepoint:

- Analysis Timepoint 1 (final analysis all data up to EOS): EOS.

## **2. STATISTICAL HYPOTHESES**

Following premature study termination, there is no formal statistical hypothesis. Only descriptive statistics will be reported.

## **3. SAMPLE SIZE DETERMINATION**

Initial sample size calculation for the primary endpoint was based on the following assumptions:

- A 2-sided Type I error of 5% and a Type II error of 10% (90% power)
- A mean change from baseline to Week 26 in RVSV of +8 mL
- A standard deviation (SD) of 20 mL for the change from baseline to Week 26 in RVSV
- A normal distribution for the change from baseline to Week 26 in RVSV
- 15% of participants with non-valuable RVSV assessment at baseline and/or postbaseline

Based on the above assumptions, a total of 80 participants (68 analyzable + 12 to account for 15% non-evaluable) must be enrolled in order to establish whether change from baseline to Week 26 in RVSV is different from zero (based on paired t-test for single arm).

The assumption that the change from baseline to Week 26 in RVSV is +8 mL is in line with literature suggesting that a difference of 8 mL to 12 mL is clinically relevant. The associated SD of 20 mL is justified by the REPAIR study interim analysis on 42 subjects, where the observed mean change (SD) from baseline to Week 26 was +16.6 mL (16.34).

After the decision to prematurely terminate the study, this sample size calculation was no longer relevant.

#### **4. POPULATIONS (ANALYSIS SETS) FOR ANALYSIS**

Analysis sets are detailed in [table 2](#) below:

**Table 2: Overview of the Different Populations for Analyses**

Analysis Sets	Description
Screened Analysis Set (SCR)	The screened analysis set (SCR) includes all participants who were screened and received a participant number.
Safety Set (SS)	The safety set (SS) includes all participants from the SCR who received at least 1 dose of study intervention.

Due to premature study termination, only the SCR and the SS will be kept.

### **5. STATISTICAL ANALYSES**

#### **5.1. General Considerations**

Following premature study termination, all analyses will be performed using descriptive statistics only. No subgroup analysis will be performed. For efficacy, only listings will be produced. For baseline characteristics and safety, the usual standard tables/listings will be produced.

#### **5.1.1. Visit Windows**

As participants do not always adhere to the protocol visit schedule, the following rules are applied to assign actual visits to analysis visits. Listed below are the visit windows and the target days for each visit. The reference day is Study Day 1. If a participant has 2 or more actual visits in 1 visit window, the visit closest to the target day will be used as the protocol visit for that visit window. The other additional visit(s) will not be used in the summaries or analyses but they can be used for determination of clinically important endpoints. If 2 actual visits are equidistant from the target day within a visit window, the later visit is used.

All assignments will be made in chronological order. Once a visit date is assigned to a visit window, it will no longer be used for a later time point except for the endpoint. Listed below ([Table 3](#)) are the analysis visit windows and the target days for each visit defined in the protocol.

**Table 3: Visit Windows**

Parameter	Time Interval (label on output)	Time Interval (Day)*	Target Time Point (Day)
Screening, Efficacy, and Safety	Screening	< 1	[-28 to 1]
Baseline visit	Baseline	<= 1	1
MRI, Echo, 6MWT, WHO FC, Risk stratification	Week 26	113 to 254	180
	Week 52	255 to 400	360
All other parameters	Week 12	2 to 112	84
	Week 26	113 to 210	180
	Week 52	211 to 400	360

\*Relative to Study Day 1

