6MWT=6-minute walking test; AE=adverse event; Echo=echocardiography; EOS=End of Study; EOT=End of Treatment; IMD=individual maintenance dose; MRI=magnetic resonance imaging; NT-proBNP=N-terminal pro-hormone brain natriuretic peptide; PAH=pulmonary arterial hypertension; SAE=serious adverse event; WHO FC=World Health Organization functional class

Footnotes:

- In principle, the maintenance dose can be reached after 8 weeks. Additional time is given to allow slower up-titration.
- Participants must NOT take the morning study intervention dose before any visit-related procedure.
- Must be signed before first study-related activity.
- For eligibility criteria based on blood laboratory results, the decision to enroll a participant can be made on the basis of local laboratory results obtained during screening; however, the blood samples must still be sent to the central laboratory for analysis.
- For females of childbearing potential (Section 10.5).
- Serum pregnancy test.

- g. Urine pregnancy test at site.
- h. Urine pregnancy test at participant's home. The site will call female participants of childbearing potential monthly to check the pregnancy test result. A window of ± 5 days for each pregnancy test/phone call will be allowed.
 - i. Test to be done within 30 to 37 days after EOT.
 - j. If MRI, Echo, 6M WT, or WHO FC assessments were done as part of routine practice in a way that fully complies with the study requirements, and within 28 days before Day 1, these data can be used for the study.
 - k. Optional in case of premature EOT before end of Week 16 (Day 112).
 - l. Only if EOT.
 - m. Participant's experience refers to the EQ-5D-3L questionnaire (Section 10.7).
 - n. For safety laboratory analyses (Section 8.4.2), NT-proBNP and biomarkers (Section 8.3.6).
 - o. If the results for the screening blood samples from the central laboratory are not available in time for Day 1 visit, an additional blood sample may be drawn to verify eligibility based on a local laboratory test.
 - p. Including premature EOT. In case of premature EOT, the EOT visit should take place within 7 days after the decision to end study intervention.
 - q. Except for month of Week 26 and Week 52.
 - r. In case of an epidemic situation or major disruptions, eg, COVID-19, the Week 26 visit may be delayed up to an additional 28 days (Week 26 +6/-2 weeks).

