  - **Maintenance:** During this period, participants will receive study intervention at their individual maintenance dose (IMD) from the start at Week 13 to EOT (scheduled at the end of Week  $52, \pm 7$  days). Monthly phone calls (except when site visits take place) from the site to the participant will be made to monitor participant's safety by collecting information on concomitant medications, AEs and SAEs. At Week 26 (Day 168 to 196), a site visit is scheduled to assess MRI, Echo, 6MWT, WHO FC, blood draw for secondary and exploratory endpoints. At Week 39 (+ 14 days), participants will return to the site for a study drug return/dispensing visit: no assessments will be performed at this site visit.
- **EOT:** EOT should occur at end of Week  $52 \pm 7$  days (Day 350 to 378). At this visit, postbaseline assessments will be performed (MRI, 6MWT, WHO FC, blood draw). In case of premature EOT before Week 16, postbaseline efficacy assessments will be optional and safety assessments will be mandatory. In case of premature EOT after Week 16, all postbaseline assessments will be performed.
- **Safety follow-up:** The safety follow-up will start the day after the last study intervention dose and end with the safety follow-up telephone call (EOS visit).
  - **EOS:** for an individual participant, EOS visit is defined as follows:
    - For participants who complete treatment or who prematurely discontinue study intervention, EOS visit is defined as the safety follow-up telephone call at least 30 days after last dose of study intervention.
    - For participants who complete treatment in the RESTORE study and who are entering another open-label clinical study with selexipag, the EOS visit is defined as the EOT visit.

- **Unscheduled visits:** Unscheduled visits will be allowed and will not be documented in the electronic case report form (eCRF); however, any AE/SAE reported during an unscheduled visit should still be recorded.

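### SAP Table 3 closes Week 26 at Day 254 for imaging but at Day 210 for labs, vital signs, NT-proBNP and EQ-5D, so one protocol-permitted delayed visit can carry two visit labels (minor)

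*SAP*

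**What the plan says.** SAP Section 5.1.1, Table 3, has two post-baseline rows. For "MRI, Echo, 6MWT, WHO FC, Risk stratification", Week 26 is Days 113-254 and Week 52 is Days 255-400. For "All other parameters", Week 26 is Days 113-210 and Week 52 is Days 211-400, with a Week 12 window of Days 2-112. The targets are Day 180 and Day 360 in both rows. NT-proBNP, EQ-5D, safety labs and vital signs are not named in the first row, so they belong to the second.

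The assignment rules in the same section are:
- "If a participant has 2 or more actual visits in 1 visit window, the visit closest to the target day will be used"; for the rest, "The other additional visit(s) will not be used in the summaries or analyses", apart from a carve-out for clinically important endpoints.
- "Once a visit date is assigned to a visit window, it will no longer be used for a later time point", with an exception for the endpoint, which is not defined there.

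At Week 26, SAP Section 1.2 says "a site visit is scheduled to assess MRI, Echo, 6MWT, WHO FC, blood draw for secondary and exploratory endpoints". Protocol Table 1 and Sections 8.4.2 and 8.6 put vital signs and EQ-5D at Week 26 too. Footnote r of Protocol Table 1 adds that, in an epidemic or major disruption, "the Week 26 visit may be delayed up to an additional 28 days", which it expresses as +6/-2 weeks.

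The SAP gives no reason for the two upper limits, and its Appendix 2 on changes to planned analyses does not mention them.

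**The concern.** A visit that the protocol accepts as Week 26 should be labelled Week 26 for everything measured at it. Under Table 3 a late but permitted visit is not: its scan is Week 26 and its blood sample is Week 52. If the participant later attends Week 52, the late safety values drop out of every by-visit summary. If not, values taken after about 30 weeks of treatment are presented as Week 52.

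This still matters after early termination, because SAP Sections 5.6.4.1 and 5.6.4.2 keep descriptive summaries by time point for labs and vital signs. The 8-item low-risk count may also be affected. It needs NT-proBNP, and SAP Section 5.4.3 leaves out anyone with a single missing component at either visit.

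**Working it through.** **Inputs.** Window limits and targets: SAP Table 3. Routine Week 26 visit, Days 168-196, and Week 52 visit, Days 350-378: SAP Section 1.2 and Protocol Section 4.1. Permitted delay: Protocol Table 1, footnote r.

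**1. The plan's own figure.** 26 × 7 = 182, and 182 ± 14 gives Days 168-196, as stated. This lies inside both Week 26 windows, so routine visits are unaffected.

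**2. Days on which the rows disagree.** Days 211-254: 254 − 211 + 1 = 44 days. On each of them the first row gives Week 26 and the second gives Week 52.

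**3. How far the permitted delay reaches.** +6 weeks = +42 days.
- From Day 182: 182 + 42 = 224, so Days 211-224 are affected (14 days).
- From target Day 180: 180 + 42 = 222, so Days 211-222 are affected (12 days).

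**4. What happens to the values in the second row.** Distance from target Day 360:

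| Visit day | Distance from 360 |
|---|---|
| 211 | 149 |
| 224 | 136 |
| 350 | 10 |
| 378 | 18 |

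A true Week 52 visit always wins, and the delayed values are set aside. Without one, they stand as Week 52.

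**5. Premature end of treatment on Days 211-254.**
- With no earlier Week 26 visit, the same split arises. Completed treatment is (211 − 1)/7 = 30.0 to (254 − 1)/7 = 36.1 weeks.
- With a routine Week 26 visit, Week 26 is filled for every parameter. That visit is at most 16 days from Day 180 (Day 168: 12; Day 196: 16), against 31 to 74 for Days 211-254. The late imaging is set aside and the late labs and vital signs become Week 52. This case bears on the cost of the fix.

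**6. The 8-item score.** Seven items follow the first row: three from the Risk Stratification form, WHO FC, 6MWD and two from Echo. NT-proBNP is the eighth.
- Narrow reading: Protocol Section 8.3.4 and the form named in SAP Section 5.4.3 cover only the three clinical items. NT-proBNP then has no Week 26 value and the score is lost.
- Broad reading: SAP Section 1.1 lists NT-proBNP under the risk-stratification objective, and the score is kept.

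The SAP does not say which applies.

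**The case against.** **Other rules might rescue the values.** SAP Section 5.6.4.1 sends each lab result to the window that fits it best, and Protocol Section 9.4.5 explains this as a way to limit missing data and accommodate visits outside their window. If fit means closeness to target, Days 211-254 belong to Week 26: Day 211 is 31 days from 180 and 149 from 360; Day 254 is 74 and 106. So a reader who infers that Week 26 must be empty for labs goes too far. But the rule may simply mean the Table 3 windows, it defines no others, and it covers labs only.

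**The once-assigned rule.** Applied parameter by parameter, it does not reach the labs. Applied to the whole visit date, it would bar the Week 52 label without giving back Week 26. A reader might conclude that the values then have no label at all. The undefined endpoint exception prevents that conclusion, since a premature end-of-treatment visit may fall under it.

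**The difference may be deliberate.** The rows do not share every visit: Echo and risk stratification are not repeated at Week 52. SAP Section 5.3.1 anticipates a premature end-of-treatment scan as the only post-baseline RVSV, which could explain a wide imaging window. A lab cut at Day 210 also keeps late end-of-treatment safety values in the summaries. These reasons are plausible but unstated. After Week 16 a premature end of treatment calls for all post-baseline assessments, so the first reason applies equally to blood samples. None of them covers the visit that footnote r permits.

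**The impact is small.** This stands. NT-proBNP, EQ-5D and the risk score appear only in listings, and labs also remain in listings and marked-abnormality summaries. SAP Section 5.6.4.2 names no vital-sign listing, but Section 5.1 promises the usual safety listings.

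**Conclusion.** The inconsistency is real and minor. Followed as written, Table 3 puts a permitted Week 26 visit on Days 211-224 (or 211-222) under Week 26 for imaging, 6MWT and WHO FC, and in the Week 52 window for NT-proBNP, EQ-5D, labs and vital signs. A premature end of treatment on Days 211-254 without an earlier Week 26 visit is split in the same way. The other assignment rules do not clearly resolve it.

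The conclusion assumes that unnamed parameters fall in the second row and that the lab rule uses the Table 3 windows. Loss of the 8-item score depends in addition on the narrow reading of risk stratification.

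A reader might infer that the efficacy results are distorted. The documents do not support that: efficacy is listed without inference or summary, and RVSV has a single window that includes every permitted delayed visit. The tables exposed are the by-visit lab and vital-sign summaries. How many participants had a visit on Days 211-254 is not stated and may be none.

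**What to change.** In SAP Table 3:
1. Move NT-proBNP and EQ-5D to the first row (Week 26 = 113 to 254, Week 52 = 255 to 400) and state that the NT-proBNP item of the risk score uses that window. Say also how values before Day 113 are labelled, since the first row has no Week 12 window.
2. For labs and vital signs, keep Week 12 = 2 to 112 and set Week 26 = 113 to 224 and Week 52 = 225 to 400. Every visit the protocol permits as Week 26 is then labelled Week 26, on either way of counting.
3. Say whether the lab rule in Section 5.6.4.1 means these windows, and define the endpoint exception in Section 5.1.1.

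**Cost.** A table edit and an update to the windowing program; no new data. After a routine Week 26 visit, end-of-treatment labs and vital signs on Days 211-224 (14 days) would leave the by-visit summaries. Labs stay in the listings and marked-abnormality summaries; a vital-sign listing should be named. NT-proBNP and EQ-5D from such a visit on Days 211-254 would lose their Week 52 label in the listings.

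**What remains.** Labs and vital signs would still differ from imaging on Days 225-254 (254 − 225 + 1 = 30 days, down from 44), which matters only for a premature end of treatment with no earlier Week 26 visit. A common cut at Day 254 would remove the split entirely, but would displace end-of-treatment safety values over all 44 days, in a study that ended early.

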### **5.1.2. Study Day and Relative Day**

Study Day 1 or Day 1 refers to the day when a participant receives the first dose of study intervention. All efficacy and safety assessments at all visits will be assigned a day relative to this date.

Study day or relative day for a visit is defined as:

- Visit date - (date of Study Day 1) +1, if visit date is  $\geq$  date of Day 1
- Visit date - Date of Day 1, if visit date  $<$  date of Day 1

There is no 'Day 0'.

### **5.1.3. Baseline**

Baseline is defined as the last observation on or before the day of the first dose of study intervention. Participants without a baseline value will be excluded from the corresponding analysis.

### **5.1.4. Up-titration period start date**

It is the first day of selexipag administration. It is derived as the first treatment start date (in chronological order) in the "Study Drug Administration" eCRF.

### **5.1.5. Up-titration period end date**

It is the date of Week 12 visit from the "Medication Kit Dispensation/ Accountability [IWRs or Balance]" eCRF form. In case of premature discontinuation or death prior to Week 12, the 'End of Treatment Date' in the "End of Treatment" eCRF form or the date of death will be considered. If both dates are missing and the subject discontinued from the study prior to Week 12, the 'End of Trial Date' from the "End of Trial" form will be used.

### **5.1.6. Maintenance period start date**

It is derived for subjects who did not discontinue the study prior to Week 12, as the day after the Week 12 visit date.

### **5.1.7. Maintenance period end date**

It is derived for subjects with maintenance period start date available.

It is the 'End of Treatment Date' in the "End of Treatment" eCRF form or the date of death (when applicable). If both dates are missing the 'End of Trial Date' from the "End of Trial" form will be used.

### **5.1.8. Imputation Rules for Missing AE Date/Time of Onset/Resolution**

Partial AE onset dates will be imputed as follows:

- If the onset date of an adverse event is missing day only, it will be set to:
  - First day of the month that the AE occurred, if month/year of the onset of AE is different than the month/year of the first dose of study treatment.
  - The day of first dose of study treatment, if the month/year of the onset of AE is the same as month/year of the first dose of study treatment and month/year of the AE resolution date is different
  - The day of first dose of study treatment or day of AE resolution date, whichever is earliest, if month/year of the onset of AE and month/year of the first dose of study treatment date and month/year of the AE resolution date are same.
- If the onset date of an adverse event is missing both day and month, it will be set to the earliest of:
  - January 1 of the year of onset, as long as this date is on or after the first dose of study treatment
  - Month and day of the first dose of study treatment, if this date is the same year that the AE occurred
  - Last day of the year if the year of the AE onset is prior to the year of the first dose of study treatment,
  - The AE resolution date.
- Completely missing onset dates will not be imputed, but the event will be assumed to be treatment emergent unless otherwise indicated.

Partial AE resolution dates not marked as ongoing will be imputed as follows:

- If the resolution date of an adverse event is missing day only, it will be set to the earliest of the last day of the month of occurrence of resolution or the day of the date of death, if the death occurred in that month.
- If the resolution date of an adverse event is missing both day and month, it will be set to the earliest of December 31 of the year or the day and month of the date of death, if the death occurred in that year.
- Completely missing resolution dates will not be imputed.

Concomitant therapy start dates will be imputed as follows:

- If the start date is missing day only, it will be set to first day of the month.
- If the start date has the year, but is missing the month, it will be set to January 1.
- If the start date is completely missing, it will not be imputed.

Concomitant therapy end dates will be imputed as follows:

- If the start date is missing day only, it will be set to last day of the month.
- If the year is supplied, but is missing the month, it will be set to December 31, or the date of death if this is earlier.
- If the start date is completely missing, it will not be imputed.

For missing or partial assessment dates:

- For scheduled visits, the date will be set to the date closest to the scheduled date, within the range allowed by the partial dates. (For screening assessments, use day -8 as the scheduled date.)
- For unscheduled visits with partial dates:
  - if the day after first dose of study treatment is within the period, it will be set to the day after first dose;
  - otherwise, if the day after first dose of study treatment is within the period, it will be set to the day of first dose;
  - otherwise, if only the day is missing, it will be set to first of the month.

otherwise, if the year is supplied, but is missing the month, it will be set to January 1.

## **5.2. Participant Dispositions**

It is permitted to re-screen subjects once, if the reason for non-eligibility was transient (e.g., abnormal laboratory test, insufficient wash-out period of a forbidden medication). All screening assessments should then be repeated at the time of re-screening.

If a subject is screened twice and then enrolled, the first screening attempt is not considered in the evaluation of screening failures.

A subject is considered a screening failure as identified from the answer 'Screen Failure' to the eCRF question 'What was the subject's status?' in the "End of Trial" form and the reason provided in the same form is used as the primary reason for screening failure.

Screened participants and reason for screen failures will be summarized overall.

A subject listing (including the inclusion criteria not met or the exclusion criteria met as collected in the "Inclusion/Exclusion Criteria Not Met" eCRF form) will be also provided for screening failures.

The number of participants in the following disposition categories will be summarized throughout the study:

- Participants who received study intervention
- Participants who completed the study (including EOS visit)
- Participants who terminated study prematurely
- Reasons for premature termination of study
- Participants who discontinued study intervention
- Reasons for discontinuation of study intervention

A listing will be provided for the following categories:

- Participants who discontinued study intervention prematurely
- Participants who terminated study prematurely

The number of subjects in each analysis set (i.e., SCR, SS) will be summarized.

A listing will be provided displaying the subject membership in the SS. This listing will be run on the SCR.

### **5.3. Primary Endpoint(s) Analysis**

Change in RVSV from baseline to Week 26 will be reported descriptively only (listing).

